Appendix V Regional Alopecia Assessment.....	73
Appendix VI Surgical Wound Complication Asessment.....	7

Study Schema

Localized, resectable soft tissue sarcoma of the extremity/limb girdle or superficial trunk

Pre-operative radiation therapy

Dose: 42.75 Gy in 15 fractions

Definitive surgical resection

(3-6 weeks interval between radiation therapy and definitive surgery)

Event Monitoring

List of Abbreviations

AE	Adverse Event/Adverse Experience
BID	Twice daily
cGy	centiGray
CRF	Case Report Form
CT	Computed Tomography
CTCAE	Common Terminology Criteria for Adverse Events
CTV	Clinical Target Volume
DSMB	Data and Safety Monitoring Board
DVH	Dose Volume Histogram
ECOG	Eastern Cooperative Oncology Group
eCRF	Electronic Case Report Form
ER / ES	Electronic Record and Electronic Signature
Gy	Gray
GTV	Gross Tumor Volume
ICRU	International Commission on Radiation Units and Measurements
IMPT	Intensity Modulated Proton Therapy
IMRT	Intensity Modulated Radiotherapy
IND / IDE	Investigational Drugs and Devices
IRB	Institutional Review Board
ITV	Internal Target Volume
LFR5	Local Failure Rate at 5 years
MCCC	Mayo Clinic Cancer Center
MRI	Magnetic Resonance Imaging
PROMISE	Patient-Reported Outcomes Measurement Information System
PS	Performance Status
PTV	Planning Target Volume
RBE	Relative Biological Effectiveness
RT	Radiation Therapy
SOC	System Organ Class
TESS	Toronto Extremity Salvage Score
UPIRTSO	Unanticipated Problems Involving Risks To Subjects or Others
VMAT	Volumetric Modulated Arc Therapy
3DCRT	3D Conformal Radiation Therapy

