2.2 Secondary Objectives

- 2.2.1 To report the 5-year local failure rate associated with hypofractionated preoperative radiation therapy, 42.75 Gy in 15 fractions.
- 2.2.2 To report the 5-year disease-free survival rate associated with hypofractionated preoperative radiation therapy, 42.75 Gy in 15 fractions.
- 2.2.3 To report the 5-year overall survival rate associated with hypofractionated preoperative radiation therapy, 42.75 Gy in 15 fractions.
- 2.2.4 To report long-term toxicity rates associated with hypofractionated preoperative radiation therapy, 42.75 Gy in 15 fractions.
- 2.2.5 To describe patterns of relapse associated with hypofractionated preoperative radiation therapy, 42.75 Gy in 15 fractions.
- 2.2.6 To describe patient reported outcomes/quality-of-life outcomes with hypofractionated preoperative radiation therapy, 42.75 Gy in 15 fractions.

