4.0 Test Schedule

	Pre-treatment/ Baseline ≤30 days prior to registration	Hypo-fractionated RT 42.75 Gy in 15 fractions	Post-RT Assessment (+/- 5 days)	Pre- Operative Assessment Within 2 weeks of surgery⁹	Post- Operative Assessment 4-8 weeks Post-Surgery^{6,9}	Years 1 & 2 Post-Surgery Assessment Every 6 Months Post-Surgery^{7,8,9} (+/- 8 weeks)	Years 3-5 Post-Surgery Assessment Annually Post- Surgery^{7,8,9} (+/- 8 weeks)
History, physical exam ⁷ , ECOG status	X		X	X		X	X
Pathology review ¹	X				X		
Primary site MRI ² , ⁵	X			X		X	X
PET/CT or CT Chest ⁵ ,	X			X		X	X
Pregnancy test ³	X						
AE Acute Assessment (See section 10.0)	X		X	X			
Hypofractionated RT		X					
CTCAE v5.0 Solicited Late Toxicity Assessment (See section 10.0)	X				X	X	X
Wound Complication Assessment (Appendix VI/Section 11.0)					X	X	
Regional Alopecia Assessment (Appendix V)	X		X	X			
Joint Stiffness Assessment (Appendix IV)	X		X	X		X	X
PROMISE-10 ^a	X			X		X ⁴	
TESS ^b	X			X		X ⁴	

1. Pathology review includes histopathologic diagnosis of soft tissue sarcoma and grade, where applicable.
2. CT is acceptable if MRI is not advisable.
3. For women of childbearing potential only. Must be done ≤7 days prior to beginning radiation treatment. Tubal ligation and IUD in place are exceptions.
4. Obtained at 12, 18, and 24 months.
5. Within 60 days of enrollment
6. Follow Up timepoints may be evaluated outside the anticipated window as deemed appropriate by Stand of Care Radiation Oncology and Orthopedic Surgery follow up schedule
 - a. Patient-Reported Outcomes Measurement Information System
 - b. Toronto Extremity Salvage Score
7. Assessments may be completed by NP/PA in person or by virtual and/or phone visit if patient is unable to return to study site.
8. Per physician discretion
9. If patient develops any type of disease progression or is unwilling to return to the institution, patients will move to yearly survival follow up. No additional assessments will need to be done.

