16.3.2 Secondary Outcome Analysis

16.3.2.1 Local failure is defined any radiographic or pathologic evidence of recurrent disease inside the CTV and/ or to within 3 cm from the edge of the CTV. In the absence of censored patients prior to 5 years, local failure rate at 5 years (LFR5) will be equal to the binomial proportion. LFR5 will be evaluated by the number of patients free of local failure/recurrence at 5 year divided by the total number of evaluable patients. Exact binomial 95%

confidence interval for the point estimate will be provided. In the case of censoring prior to 5 years, LFR5 will be estimated using the Kaplan-Meier method.

- 16.3.2.2 Disease-Free Survival is defined as the time from registration date to the earliest date of documentation of either, local recurrence, regional recurrence, distant recurrence, or death due to any cause, censoring patients who are alive and local recurrence free at the date of last known clinical assessment. The distribution of disease-free survival will be estimated using method of Kaplan-Meier.
- 16.3.2.3 Overall Survival is defined as the time from registration date to death due to any cause, censoring patients alive at the date of last contact. The distribution of overall survival will be estimated using method of Kaplan-Meier.
- 16.3.2.4 Late toxicity is defined as toxicity occurs any time between 3 months and 24 months after completion of hypofractionated preoperative radiation therapy. The rate of \geq grade 2 late toxicities will be estimated by the number of patients with a \geq grade 2 late toxicity divided by the total number of evaluable patients. Exact binomial 95% confidence intervals for the true rate of \geq grade 2 toxicity events will be calculated.
- 16.3.2.5 Pattern of relapse will be evaluated by number of patients with patterns of tumor recurrence such as local recurrence, marginal recurrence, regional recurrence, distant metastasis, and second primary tumor divided by the total number of evaluable patients. Exact binomial 95% confidence interval for the point estimate will be provided.
 - 16.3.2.5.1 Local tumor recurrence is defined as any tumor recurrence inside the CTV.
 - 16.3.2.5.2 Marginal tumor recurrence is defined as any tumor recurrence beyond the CTV to within a 3 cm distance from the edge of the CTV.
 - 16.3.2.5.3 Distant tumor recurrence is defined as any tumor that develops distantly from the primary site of sarcoma.

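### Section 16.3.2.1 computes the 5-year local failure rate from patients without failure, and the DFS censoring clause in 16.3.2.2 is narrower than its event list (minor; secondary endpoints only)

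*Combined protocol and SAP*

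**What the plan says.** All references are to the combined protocol and SAP.

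**Local failure.** The List of Abbreviations expands LFR5 as "Local Failure Rate at 5 years", and objective 2.2.1 is "To report the 5-year local failure rate associated with hypofractionated preoperative radiation therapy". Section 16.3.2.1 defines local failure as recurrence inside the CTV or within 3 cm of its edge, and then gives two estimators:

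- Without censoring: "In the absence of censored patients prior to 5 years, local failure rate at 5 years (LFR5) will be equal to the binomial proportion". The next sentence defines that proportion: "LFR5 will be evaluated by the number of patients free of local failure/recurrence at 5 year divided by the total number of evaluable patients". An exact binomial 95% interval is to accompany it.
- With censoring: "In the case of censoring prior to 5 years, LFR5 will be estimated using the Kaplan-Meier method".

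No time origin is given for LFR5. DFS and overall survival, in 16.3.2.2 and 16.3.2.3, both run from registration.

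**Disease-free survival.** Section 16.3.2.2 lists four events: local recurrence, regional recurrence, distant recurrence, and death from any cause. Time runs to whichever is documented first. The censoring clause then covers patients who are living and have had no local recurrence; it does not mention regional or distant recurrence.

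**Follow-up.** Section 4.0 schedules assessments through the column "Years 3-5 Post-Surgery Assessment". Footnote 9 of that table adds: "If patient develops any type of disease progression or is unwilling to return to the institution, patients will move to yearly survival follow up". It continues: "No additional assessments will need to be done".

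**The concern.** Two stated rules give a wrong result if followed to the letter. The LFR5 formula counts the patients who did not fail and labels the result a failure rate. The DFS censoring clause lets a patient who already has a listed event also qualify for censoring.

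The stake is the accuracy of two reported secondary results. Section 1.0 cites a 5-year local recurrence rate of at most 10% as background, so readers will set LFR5 beside that figure. A programmer working from the text alone should not have to guess the direction of the proportion, the starting point of the clock, or which rule wins when two apply.

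**Working it through.** **Plan's own figure.** The plan states no target, sample size or power for LFR5 or DFS. Its only sample-size figure, for the primary endpoint in 16.2, reproduces: n = [(1.2816 × √(0.45 × 0.55) + 0.8416 × √(0.35 × 0.65)) / 0.10]² = 107.95, rounded up to 108; and 108 / 0.90 = 120. Nothing below changes it. I use 108 as the LFR5 denominator for illustration.

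**Step 1: direction of the LFR5 formula.** Assume 11 local failures in 108, close to the 10% background rate.

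| Quantity | Calculation | Result | Exact 95% CI |
|---|---|---|---|
| Failure rate, as named | 11/108 | 10.2% | 5.2% to 17.5% |
| Formula as written | (108 − 11)/108 = 97/108 | 89.8% | 82.5% to 94.8% |

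The two are exact complements, so each can be recovered from the other by subtraction.

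**Step 2: when the formula governs.** It applies only if nobody is censored before 5 years. If each of 108 patients independently has probability p of such censoring, the chance of none is (1 − p)^108: 34% for p = 1%, 0.4% for p = 5%, and 0.001% for p = 10%. These values of p are assumptions. The Kaplan-Meier sentence is therefore the one likely to be used. That sentence is not inverted. It leaves 1 − S(5) to convention and gives no time origin.

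**Step 3: the DFS rules side by side.** Take a living patient with a distant recurrence and no local recurrence.

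- Event list: event, dated at the distant recurrence.
- Censoring clause read literally: living and without local recurrence, so censored at the last clinical assessment.

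Both rules fit. Because time runs to the first documented event, the first reading is very probably intended.

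**Step 4: sensitivity to footnote 9.** Section 16.3.2.1 does not say how LFR5 treats a patient whose local status stops being assessed after a regional or distant relapse. Assume constant hazards and net 5-year probabilities of 10% local failure, 5% death without progression, and P = 20%, 30% or 40% regional or distant progression. This gives λ_L = −ln(0.90)/5 = 0.0211 and λ_P = −ln(1 − P)/5. Deaths are censored, as the plan's Kaplan-Meier estimate implies.

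- Censored at the last local assessment: 1 − S(5) = 1 − exp(−5λ_L) = 10.0%.
- Left at risk but unassessed: only failures before progression are seen, so the hazard entering Kaplan-Meier is λ_L × (unprogressed at risk)/(all at risk), accumulated over 5 years.

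| Assumed survival after progression | P = 20% | P = 30% | P = 40% |
|---|---|---|---|
| Same death hazard as other patients | 9.0% | 8.4% | 7.9% |
| Median 2 years | 9.3% | 9.0% | 8.6% |
| Median 1 year | 9.6% | 9.3% | 9.0% |

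Leaving such patients at risk lowers the estimate by about 0.4 to 2 points. The interval in Step 1 is about 12 points wide (17.5 − 5.2 = 12.3).

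**The case against.** The case for leaving this alone is strong on consequence. The name, the abbreviation and the objective all fix the direction of LFR5, and the inverted formula belongs to a branch that will hardly ever apply. Section 16.3.2.5 counts local and marginal recurrences the right way round, as patients with the event over evaluable patients. Together those categories cover the 16.3.2.1 event, although not at a fixed 5 years. A failure rate from Kaplan-Meier is conventionally 1 − S(t). A patient with distant relapse already has a DFS event under the first-event rule. All of this stands, and it keeps the point minor. It does not make the two sentences correct.

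Stronger readings are tempting, and the documents do not support them:

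- **Expecting LFR5 to be reported near 90%.** This needs both the no-censoring branch and a failure to notice that the label contradicts the number.
- **Claiming DFS would be inflated.** If every non-local relapse were censored (assuming 10% local failure, 20% to 40% non-local relapse and no deaths), 5-year DFS would read 90% instead of 72% to 54% (0.90 × 0.80 to 0.90 × 0.60). That requires ignoring the first-event rule.
- **Reading footnote 9 as proof that local status goes unassessed after relapse.** It removes a requirement and does not forbid assessment. Sections 13.0 and 19.0 leave routine care in place. Leaving unassessed patients at risk is not a reading the text invites; censoring at the last assessment is ordinary practice.
- **Treating the absence of a competing-risk estimate as an error.** The event is recurrence only and the plan names Kaplan-Meier. Cumulative incidence is an alternative method, not another reading of the text.
- **Inferring censoring from the 10% loss in 16.2.2 or the 8-week visit window.** The 10% supports the 12 patients added above the 108 evaluable. The window produces early censoring mainly if the clock starts at surgery. From registration, surgery falls roughly 6 to 12 weeks later, so a year-5 visit 8 weeks early lands between 2 weeks before and 4 weeks after 5 years.

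**Conclusion.** Two sentences are wrong as written. In 16.3.2.1 the numerator is the complement of the endpoint (89.8% in place of 10.2% in the illustration of 11 failures in 108). In 16.3.2.2 the censoring clause overlaps the event list for living patients with only regional or distant recurrence. The intended meaning is clear for the first and likely for the second, so the realistic effect on reported results is small.

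The unstated time origin, 1 − S(5) and the rule after footnote 9 are missing detail, not errors. The last is worth about 0.4 to 2 points of LFR5 under assumed hazards, progression rates and survival after progression, none of which come from the documents.

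Severity is minor. Both endpoints are descriptive, with no target, test or decision attached. The primary endpoint, the 108 and 120 patients, the power and the decision rule are unaffected.

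**What to change.** **Corrections**

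- 16.3.2.1: make the numerator patients with local failure by 5 years. For the censored case, write LFR5 = 1 − S(5), with S the Kaplan-Meier estimate, and state the time origin (registration, as for DFS and overall survival, or surgery).
- 16.3.2.2: censor patients who are alive and free of local, regional and distant recurrence.

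**Optional clarifications**

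- State that a patient whose local status is no longer assessed once footnote 9 applies is censored for LFR5 at the last local assessment. Note that this assumes the local failure risk is unrelated to the relapse that ended assessment.
- Report, as a supplement, the 5-year cumulative incidence of local failure with death without local failure as a competing event.
- Align the heading of 11.2, which speaks of survival, with its recurrence-only definition.

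The cost is a few sentences and standard software. The date of last local assessment comes from the scheduled imaging and examinations. No visits are added and the sample size does not change.

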1.0 Background and Rationale

Approximately 12,000 patients are diagnosed with soft tissue sarcomas annually in the United States, accounting for 1% of all adult malignancies.¹ Given the rarity, diversity (> 60 different histologies), and treatment complexity associated with soft tissue sarcomas, patients routinely undergo treatment at specialty centers. Historically, extremity soft tissue sarcomas were treated with amputation. Advances in radiation therapy and surgical techniques, however, have made radiation therapy plus limb-salvage surgery the standard treatment for most localized, extremity soft tissue sarcomas.²⁻⁵ Superficial trunk soft tissue sarcomas are treated in a similar fashion. With this multi-modal treatment approach, the 5 year local recurrence rate for extremity and superficial trunk soft tissue sarcomas is $\leq 10\%.$ ⁶

Radiation therapy can be administered preoperatively, intraoperatively, postoperatively, or as a combination of the aforementioned.^{2,3,7} Preoperative radiation therapy is associated with a higher acute wound complication rate compared to postoperative radiation therapy.⁶ O'Sullivan et. al. reported a 35% acute wound complication rate with preoperative radiation therapy compared to a 17% rate with postoperative radiation.⁶ Acute wound complication was defined as a major wound issue requiring an invasive intervention (i.e., second surgery or hospitalization for wound care) within 3 months of surgery.⁶ Several other reports document similar acute wound complication rates.⁸⁻¹²

Many centers in the United States and abroad favor pre-operative radiation therapy due to the lower total radiation dose administered (50 Gray (Gy) versus 60-66 Gy) and smaller treatment volume compared to postoperative radiation therapy. These aspects are thought to contribute to the lower irreversible, long-term toxicity rates seen with preoperative radiation therapy.^{13,14} Davis et. al. reported more frequent rates of fibrosis (48.2% versus 31.5%), edema (23.2% versus 15.1%), and joint stiffness (23.2% versus 17.8%) with postoperative radiation therapy compared to preoperative radiation therapy.¹⁴ Higher rates of irreversible, long-term toxicities adversely affect patient function.^{13,14} Lastly, preoperative radiation therapy optimizes the chances of obtaining a margin-negative resection and may decrease the potential for metastatic cell spread at time of surgery.^{6,8,15}

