11.0 Treatment Evaluation/Measurement of Effect

- 11.1 Development of a surgical wound complication: Secondary unplanned operation under general or regional anesthesia for wound repair (e.g., debridement, operative drainage, or secondary wound closure including rotationplasty, free flaps or skin grafts); or wound management without secondary operation including invasive procedures (e.g., aspiration of seroma or readmission for wound care such as intravenous antibiotics or persistent deep packing for 120 days or longer).
- 11.2 Local recurrence free survival: Any radiographic or pathologic evidence of recurrent disease inside the CTV and/or beyond the CTV to within a 3 cm distance from the edge of the CTV. Ideally assessed by radiographic imaging in comparison to the treatment fields in order to determine site of recurrence.

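### The 5-year local failure rate is to be estimated by Kaplan-Meier with recurrence as the only event and no rule for death, so it would estimate a net risk at or above the proportion of patients who fail locally

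*Combined protocol and SAP*

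**What the plan says.** Objective 2.2.1 is descriptive: "To report the 5-year local failure rate associated with hypofractionated preoperative radiation therapy, 42.75 Gy in 15 fractions".

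Section 16.3.2.1 gives the definition and two estimators:

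- Definition: "Local failure is defined any radiographic or pathologic evidence of recurrent disease inside the CTV", extended to 3 cm beyond the CTV edge. Death is not mentioned.
- Without censoring: "In the absence of censored patients prior to 5 years, local failure rate at 5 years (LFR5) will be equal to the binomial proportion". The formula that follows is: "LFR5 will be evaluated by the number of patients free of local failure/recurrence at 5 year divided by the total number of evaluable patients". An exact binomial 95% interval goes with it.
- With censoring: "In the case of censoring prior to 5 years, LFR5 will be estimated using the Kaplan-Meier method". No interval method is named for this branch, and no time origin is given for local failure.

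The next item, disease-free survival, does include death. Its events are "local recurrence, regional recurrence, distant recurrence, or death due to any cause, censoring patients who are alive and local recurrence free" at last assessment. Overall survival likewise has a death event and a censoring rule. Local failure has neither.

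Section 11.2 labels the same endpoint differently: "Local recurrence free survival: Any radiographic or pathologic evidence of recurrent disease inside the CTV". The label suggests that death counts, but the definition under it lists recurrence only. Neither competing risks nor cumulative incidence appears anywhere in the documents.

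Footnote 9 to the test schedule (section 4.0) moves patients with progression of any kind to annual survival follow-up, with no further study assessments.

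**The concern.** A patient who dies without local recurrence can no longer have one. Kaplan-Meier with recurrence as the only event censors that patient at death and treats the remaining risk as if it continued. One minus Kaplan-Meier then estimates a net risk, the risk in a hypothetical setting where nobody dies first. The objective asks for something else: the proportion of treated patients who fail locally.

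The Kaplan-Meier branch is the one that will be used. The binomial branch needs every patient uncensored to 5 years, and some deaths or losses over that period are practically certain. The two branches also need not estimate the same quantity. The binomial denominator keeps patients who died, while Kaplan-Meier removes them from the risk set at death.

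Section 1.0 argues for the dose partly from local failure rates: at most 10% at 5 years historically, 11% at 3 years with one short course, and 19% at a median follow-up of 35 months with another. Readers will set the trial's figure beside these, so what it estimates should be clear.

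**Working it through.** **Plan's own figure.** The plan states no target, precision or power for LFR5, so there is nothing to reproduce. The 10% below is taken from section 1.0 as an illustrative true incidence.

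**Inputs.** True 5-year cumulative incidence of local failure: 10%. Net 5-year risk of death without local failure, d: 20%, 30% or 40%. The values of d are assumptions, because the documents give no death rate. Hazards are taken as constant.

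**Formulas.** Let H1 and H2 be the 5-year cumulative hazards of local failure and of death without local failure.

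- H2 = −ln(1 − d)
- Cumulative incidence of local failure = H1/(H1+H2) × [1 − exp(−(H1+H2))], set to 0.10 and solved for H1
- One minus Kaplan-Meier with deaths censored = 1 − exp(−H1)
- Crude proportion dying without local failure = H2/(H1+H2) × [1 − exp(−(H1+H2))]

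| d (net) | H2 | H1 | True incidence | One minus KM | Excess (points) | Crude proportion dying without local failure |
|---|---|---|---|---|---|---|
| 20% | 0.2231 | 0.1180 | 10.0% | 11.1% | 1.1 | 18.9% |
| 30% | 0.3567 | 0.1261 | 10.0% | 11.8% | 1.8 | 28.3% |
| 40% | 0.5108 | 0.1358 | 10.0% | 12.7% | 2.7 | 37.6% |

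For the first row, H1+H2 = 0.3412 and 1 − exp(−0.3412) = 0.2891. Then 0.1180/0.3412 × 0.2891 = 0.100, and 1 − exp(−0.1180) = 0.111.

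If 20%, 30% and 40% are instead the crude proportions q dying without local failure, then with c the true incidence, one minus Kaplan-Meier = 1 − (1 − c − q)^(c/(c+q)). With c = 10% this gives 11.2%, 12.0% and 12.9%. At c = 19% it gives 21.4%, 23.0% and 25.0%.

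**Timing.** Take 108 patients followed completely, with 11 local failures (11/108 = 10.2%) and 22 deaths without local failure:

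- All local failures before all deaths: one minus Kaplan-Meier = 11/108 = 10.2%, no excess.
- Both spread evenly over years 0 to 5: 11.4%, an excess of 1.3 points before rounding.
- All deaths before all local failures: 108 − 22 = 86 remain at risk and 11/86 = 12.8%, an excess of 2.6 points.

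The Aalen-Johansen estimate is 10.2% in all three cases. With complete follow-up it equals the crude failure proportion.

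**The section 11.2 label taken literally.** If death were an event, the complement of local-recurrence-free survival would be local failures plus deaths. In the first row of the table that is 10.0% + 18.9% = 28.9%, much further from the local failure rate.

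**The binomial numerator.** It counts patients free of failure. With 11 failures in 108 it gives 97/108 = 89.8%, the complement of a failure rate.

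**The case against.** **Censoring of deaths is inferred.** The plan never says that deaths are censored for this endpoint. Its stated censoring rules, for disease-free and overall survival, cover only patients who are alive. That is correct, and one could say that the handling of death is merely unspecified. But recurrence is the only event in both 16.3.2.1 and 11.2, and Kaplan-Meier applied to that definition has to censor deaths. The alternative reading, with death as an event, overstates local failure more.

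**The effect is small and rests on assumptions.** At 10% and n = 108 the standard error is √(0.1 × 0.9/108) = 2.9 points, so the shifts in the table lie within sampling error. No decision rests on LFR5: it has no threshold, test or stopping rule, and the decision rule in 16.2.1 uses wound complications only. All of this stands and limits the weight of the point. A systematic shift with a cheap remedy is still worth removing.

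**A reader might infer that the plan could push a regimen that meets the 10% benchmark above it.** The documents do not support that. Section 1.0 states that "the 5 year local recurrence rate for extremity and superficial trunk soft tissue sarcomas is" at most 10%, but not how that figure was estimated. If it came from Kaplan-Meier, then Kaplan-Meier is the like-for-like comparison, and switching would flatter the new regimen. The 11% and 19% figures are not 5-year rates.

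**A reader might also infer that the reported rate will simply be too high.** Footnote 9 works the other way. Patients with distant progression, who are likely to be among those who later die, stop having study assessments, and a later local failure may go unrecorded. The net direction of error is therefore not known.

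**Section 16.3.2.5 partly covers the gap.** It reports local and marginal recurrence as proportions of all evaluable patients, which keeps deaths in the denominator. It does not handle incomplete follow-up, so it does not replace a competing-risks estimate.

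**Conclusion.** The point holds as a choice of estimator. Followed as written, 16.3.2.1 gives a net risk that is at or above the proportion of patients who fail locally. For a true 10% and constant hazards, the excess is about 1.1, 1.8 or 2.7 points at assumed net 5-year death risks of 20%, 30% or 40%. It falls to zero if local failures all come before deaths. These sizes concern the estimator alone and assume that every local failure is recorded, which footnote 9 puts in doubt.

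The sample size, type I error rate and primary conclusion are untouched. What is affected is the meaning of a descriptive secondary result and its comparability with the historical rates. The documents do not show that the shift would change how the regimen is judged against 10%.

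**What to change.** 1. In 16.3.2.1, estimate LFR5 as the Aalen-Johansen cumulative incidence of local failure at 5 years, with death without local failure as the competing event. Give a 95% confidence interval and state the time origin.
2. Replace the binomial formula, whose numerator counts patients free of failure. No separate branch is needed, because with complete follow-up Aalen-Johansen equals the crude failure proportion.
3. Retitle 11.2 as local failure, so that label and definition agree.
4. Report one minus Kaplan-Meier as a labelled sensitivity figure for comparison with older series.
5. State how the analysis handles patients whose assessments stop after distant progression under footnote 9 of section 4.0, and acknowledge that local failures missed there bias LFR5 downward.

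Items 1 to 4 cost SAP wording and a standard routine, with no new data. Their one drawback is less direct comparability with Kaplan-Meier series, which item 4 covers. Item 5 also needs only wording, but stating the rule does not recover unrecorded local failures, and neither does the change of estimator.

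### The DFS rule counts deaths during survival-only follow-up but censors survivors at their last clinic visit, so the Kaplan-Meier risk set after leaving clinic depends on who later dies

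*Combined protocol and SAP*

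**What the plan says.** Five-year DFS is a secondary objective (2.2.2). Section 16.3.2.2 lists the events as "local recurrence, regional recurrence, distant recurrence, or death due to any cause", with no limit on the time between the last disease assessment and a death. Event-free survivors are handled by "censoring patients who are alive and local recurrence free at the date of last known clinical assessment", and "The distribution of disease-free survival will be estimated using method of Kaplan-Meier". The next item, 16.3.2.3, uses a later date for OS: "censoring patients alive at the date of last contact".

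Footnote 9 of the section 4.0 schedule creates a group for whom the two dates differ: "If patient develops any type of disease progression or is unwilling to return to the institution, patients will move to yearly survival follow up". It continues: "No additional assessments will need to be done". Footnote 7 of the same schedule allows assessments "by virtual and/or phone visit if patient is unable to return to study site". No sensitivity analysis for DFS is planned.

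**The concern.** A patient who progressed before moving to survival follow-up is already a DFS event, so the problem lies with those who stop returning while recurrence-free. If such a patient dies, the death is learned of and counted on its date. If the patient lives, the follow-up is cut back to the last clinic assessment, possibly years earlier. Kaplan-Meier needs membership of the risk set at time t not to depend on what happens after t; here it does.

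The trial has one arm, and section 1.0 sets its oncologic outcomes against historical standards. No control group exists in which the same artefact would cancel. Section 16.3 also plans an exploratory comparison of secondary outcomes between proximal lower limb and other sites, where unequal attrition could produce a difference that is not real.

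**Working it through.** **No DFS figure to reproduce.** The plan gives no assumed DFS, OS or rate of refusal to return, and no length for the yearly survival follow-up. The 10% loss in section 16.2.2 refers to the 120-day wound endpoint. The inputs below are therefore assumptions, shown as ranges.

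**The rule as written.** Take a recurrence-free leaver with last assessment at time a, death at D, and survival follow-up to f.
- If D ≤ f: time D, event.
- If D > f: time a, censored.

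Among leavers still at risk at any t > a, every one has D ≤ f, so all of them become events. That pushes the estimate down. A weaker force pushes it up: recurrences after leaving are not seen, so a failure is dated late (at death) or missed.

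**How many patients.** Assume true 5-year DFS of 60% and a nominal 20% leaving by year 5, both exponential.
- DFS hazard: −ln(0.60)/5 = 0.1022 per year.
- Leaving hazard: −ln(0.80)/5 = 0.0446 per year.
- Leaving event-free by year 5: 0.0446/(0.0446 + 0.1022) × (1 − 0.80 × 0.60) = 0.158.
- Of 108 patients: 0.158 × 108 ≈ 17.

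A nominal 20% is thus about 16% of patients. In simulation about 2 of them die and count as events, and about 15 are removed back to their last visit.

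**Size when leaving is unrelated to prognosis.** Simulation with disease status observed continuously until leaving, follow-up to 5 years, true DFS 60% and OS 75%:

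| Nominal leaving | Written rule | All leavers censored at last assessment | Written minus true 60.0 |
|---|---|---|---|
| 10% | 59.3 | 60.0 | −0.7 |
| 20% | 58.5 | 60.0 | −1.5 |
| 30% | 57.5 | 60.0 | −2.5 |

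Other settings gave −0.9 to −3.1 points at DFS 50%/OS 65% and −0.5 to −1.8 at DFS 70%/OS 85%.

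A second simulation dated the last assessment to the section 4.0 visits (true DFS 60–70%, death without recurrence 0.01–0.03 per year, death after recurrence 0.35 per year). It gave shortfalls of about 0.8–1.0, 1.7–2.1 and 2.9–3.5 points; a repeat gave 0.7–1.0, 1.7–2.3 and 2.9–3.7. Part of this is not due to the two cut-offs: censoring every leaver at the last visit still fell short by up to about 0.9 point, because censoring is dated back to a visit.

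**Length of survival follow-up.** With a common data cut at 5 to 7.5 years the shortfall was about 0.4–2.2 points. If follow-up ran without end, every leaver would eventually be a death, and at DFS 60% the written rule would give 60.9, 61.9 and 62.9, which is too high.

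**Size when leaving is related to prognosis.** Leaving hazard multiplied for patients who fail within 5 years (DFS 60%/OS 75%, 10–30% nominal leaving), points from truth:

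| Multiplier | Written rule | All leavers censored at last assessment |
|---|---|---|
| 1.5 | −0.4 to −1.6 | +0.7 to +2.3 |
| 2 | −0.1 to −0.8 | +1.3 to +4.4 |
| 3 | +0.6 to +0.8 | +2.7 to +8.2 |

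For example, at multiplier 3 and 30% leaving, the right-hand column is 68.2 − 60.0 = 8.2. In a separate run with leaving 5 times likelier in the year before an event, the written rule was between 0 and about 2 points low, and censoring all leavers ran up to about 6 points high.

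**Scale.** The 95% half-width at n = 108 and DFS 60% is 1.96 × √(0.60 × 0.40/108) = 0.092, about 9 points.

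**The case against.** The strongest reply is that the written rule is not reliably biased in one direction. A reader might infer that 5-year DFS will simply be too low, and that the shortfall reflects travel and convenience. The documents support neither: footnote 9 gives no reason for unwillingness to return, and the net error can vanish or reverse if patients nearing an event leave more often. This stands, and the downward direction must be stated as conditional.

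Footnote 7 lets patients who cannot travel be assessed remotely, and criterion 3.1.9 requires willingness to return during active monitoring. Both reduce the number affected. Footnote 7, however, is for patients unable to return, while footnote 9 covers those unwilling, so the asymmetry remains.

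Censoring every leaver at the last assessment looks like the clean repair. It is right only if leaving is unrelated to prognosis. Otherwise it discards known deaths and can flatter the regimen by more than the written rule errs.

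Finally, censoring at last known recurrence status while still counting every death leaves some asymmetry between contacts. That is true, but the interval is short, and in simulation this rule stayed within about 0.3 point of truth in every scenario.

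**Conclusion.** The inconsistency is real and follows from the plan's own text: deaths are counted to the end of survival follow-up, but survival on that track earns no follow-up time. Under leaving unrelated to prognosis, and survival follow-up ending near 5 years, 5-year DFS is understated by roughly 1, 2, and 3 to 4 points at nominal leaving of 10%, 20% and 30%, with up to about 0.9 point of that due to visit dating. All of these inputs are assumed.

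A reader might infer that the error threatens the trial's conclusion. It does not: section 16.2.1 decides on wound complications alone, objective 2.2.2 only reports DFS, and the bias is smaller than the sampling error. The confidence interval does not reflect it, however, and it is cheap to avoid. Severity is minor to moderate.

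**What to change.** 1. In section 4.0, footnote 9: at the yearly survival contact already planned, record recurrence status (local, regional, distant) and date, from the patient or from outside records.
2. In 16.3.2.2: censor DFS at the last date on which recurrence status is known. Count as events recurrences learned at contact and all deaths.
3. Where recurrence status cannot be obtained, keep the written rule. Report as a sensitivity analysis the version that censors all such patients at their last clinical assessment whether or not they later die. Do not make that version primary, because it can overstate DFS if leaving is related to prognosis.
4. Report how many patients moved to survival-only follow-up while recurrence-free, and when.

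The cost is one question at an existing contact and a few sentences in 16.3.2.2. The downside is that recurrence learned by contact or from records is dated less exactly than on scheduled imaging.
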